7.3.3.5 Is a congenital anomaly/birth defect

7.3.3.6 Is an important medical event
Any event that does not meet the above criteria, but that in the judgment of the investigator jeopardizes the patient, may be considered for reporting as a serious adverse event. The event may require medical or surgical intervention to prevent one of the outcomes listed in the definition of "Serious Adverse Event".
For example: allergic bronchospasm requiring intensive treatment in an emergency room or at home; convulsions that may not result in hospitalization; development of drug abuse or drug dependency.

7.4 Steps to Determine If an Adverse Event Requires Expedited Reporting

Step 1: Identify the type of adverse event

Step 2: Grade the adverse event

Step 3: Determine whether the adverse event is related to the protocol therapy

Attribution categories are as follows:

- Definite – The AE is *clearly related* to the study treatment.
- Probable – The AE is *likely related* to the study treatment.
- Possible – The AE *may be related* to the study treatment.
- Unrelated – The AE is *clearly NOT related* to the study treatment.

Note: This includes all events that occur within 30 days of the last dose of protocol treatment. Any event that occurs more than 30 days after the last dose of treatment and is attributed (possibly, probably, or definitely) to the agent(s) must also be reported accordingly.

Step 4: Determine the prior experience of the adverse event.

Expected events are those that have been previously identified as resulting from administration of the agent. An adverse event is considered unexpected, for expedited reporting purposes only, when either the type of event or the severity of the event is not listed in:

- the current known adverse events listed in the Agent Information Section of this protocol;
- the drug package insert;
- the current Investigator's Brochure

7.5 Reporting Requirements for Adverse Events

7.5.1 Expedited Reporting

- The Principal Investigator must be notified within 24 hours of learning of any serious adverse events, regardless of attribution, occurring during the study or within 30 days of the last administration of the study drug.
- The office of Risk Management and the IRB must be notified within 10 business days of "any unanticipated problems involving risk to subjects or others" (UPR/UPIRSO).

Insert your local requirements below:

The following events meet the definition of UPR:

1. Any serious event (injuries, side effects, deaths or other problems), which in the opinion of the Principal Investigator was unanticipated, involved risk to subjects or others, and was possibly related to the research procedures.
2. Any serious accidental or unintentional change to the IRB-approved protocol that alters the level of risk.
3. Any deviation from the protocol taken without prior IRB review to eliminate apparent immediate hazard to a research subject.
4. Any new information (e.g., publication, safety monitoring report, updated sponsor safety report), interim result or other finding that indicates an unexpected change to the risk/benefit ratio for the research.
5. Any breach in confidentiality that may involve risk to the subject or others.
6. Any complaint of a subject that indicates an unanticipated risk or that cannot be resolved by the Principal Investigator.

For IND/IDE trials: The FDA should be notified within 7 business days of any unexpected fatal or life-threatening adverse event with possible relationship to study drug, and 15 business days of any event that is considered: 1) serious, 2) unexpected, and 3) at least possibly related to study participation.

7.5.2 Routine Reporting

- All other adverse events- such as those that are expected, or are unlikely or definitely not related to the study participation- are to be reported annually as part of regular data submission.

7.6 Unblinding Procedures

Unblinding to occur in the case of serious morbidity or life-threatening illness that may be reasonably attributable to administration of misoprostol, including but not limited to admission to the intensive care unit, hyperpyrexia and repeated or high-grade fevers. While the safety of the subject always comes first, it is still important to seriously consider if unblinding the study therapy is necessary to ensure a subject's safety.

7.7 Stopping Rules

This study involves a one-time pre-operative intervention prior to a planned surgical procedure. If a patient develops immediate, intolerable side effects including but limited to emesis, diarrhea, or heavy vaginal bleeding following buccal administration of misoprostol or placebo, therapy will be discontinued.

8.0 DRUG/DEVICE INFORMATION

8.1 Agent/Device: Misoprostol

- Other names for the drug(s)/device: Cytotec
- Classification - type of agent/device: medication, synthetic Prostaglandin E1 analogue
- Mode of action: Production of uterine contractions
- Storage and stability: Store at or below 25°C (77°F), in a dry area.

- Protocol dose: 400mcg
- Preparation: Tablet
- Route of administration for this study: Buccally, 200mcg on each side
- Incompatibilities: Pregnancy, history of adverse reaction to prostaglandins
- Availability: Commercially available
- Side effects: A brief summary of the adverse events most likely to occur in this study and associated with this agent should be inserted here. Refer the reader to the agent's package insert or Section 7.1 above for a comprehensive list of adverse events.
- Nursing implications: Ensure patient has a negative pregnancy test and confirm list of allergies prior to providing the medication. Day of surgery urine pregnancy testing and verbal confirmation of a patient's allergies are both standard of care practices for reproductive age women undergoing surgery.

8.2 Agent/Device: Vitamin B6

- Other names for the drug(s)/device: Pyroxidine
- Classification - type of agent/device: medication, synthetic vitamin
- Mode of action: Vitamin B6 in coenzyme forms performs a wide variety of functions in the body and is extremely versatile, with involvement in more than 100 enzyme reactions, mostly concerned with protein metabolism (12).
- Storage and stability: Store at or below 25°C (77°F), in a dry area.
- Protocol dose: 100mg
- Preparation: Tablet
- Route of administration for this study: Buccally, 50 mg on each side
- Incompatibilities: none
- Availability: Commercially available
- Side effects: none
- Nursing implications: none

8.1.1 Return and Retention of Study Drug/Device

Active medication will be purchased on a case by case basis from NMH inpatient research pharmacy such that excess misoprostol is not anticipated. In the event of access active medication, this will be disposed per pharmacy protocol.

8.1.2

Compliance with administration will be documented by pre-operative nursing staff.

9.0 CORRELATIVES/SPECIAL STUDIES

N/A.

10.0 STATISTICAL CONSIDERATIONS

10.1 Study Design/Study Endpoints

This is a double blinded randomized, controlled trial of women undergoing either an abdominal and laparoscopic myomectomy at a single university-affiliated tertiary care center. Women ages 18-50 years of age with clinically documented, sonographic evidence of uterine fibroids being scheduled for abdominal myomectomy were eligible for inclusion. Eligible participants will be randomized to receive preoperative 400cg buccal misoprostol or placebo on the basis of total fibroid volume, location (intramural or subserosal) and parity. Stratification by fibroid volume (or fibroid size) will be performed prior to randomization. Fibroid volume is defined as the cumulative volume of intramural and subserosal fibroids as measured on preoperative magnetic resonance imaging (MRI), or in the instance of patient contraindication to MRI, transvaginal ultrasound (TVUS). The data collection sheet (addendum) and chart of study variables below include definition of this variable and allow for ease of recording and tracking of this variable in our study database. Women with a history of gynecologic malignancy, critical anemia or blood dyscrasias and those with a history of prior myomectomies will be excluded.

List of Study Variables to be Collected:

Outcomes	Type	Definition
Estimated blood loss	Continuous	Intraoperative blood loss as estimated by intraoperative anesthesiologists and surgeons.
% drop in Hgb	Continuous	Ratio of the drop in hemoglobin over the starting hemoglobin ($Hg_{post-op} - Hg_{pre-op}$)/ Hg_{pre-op}
Duration of hospital stay (days)	Continuous	Number of days inpatient following abdominal myomectomy.
Duration of procedure (minutes)	Continuous	Number of days inpatient following abdominal myomectomy.
Post-op fever	Dichotomous	If patient has one Temperature >101.4 or two temperatures >100.4 , then yes. If not then no.
Adverse reaction to misoprostol	Dichotomous	If patient experiences vaginal bleeding, vomiting or diarrhea then yes. If not then no.

Exposures	Type	Definition
Pre-op Misoprostol	Dichotomous	If women randomized to receive misoprostol, then yes. If women randomized to placebo, then no.

Covariates	Type	Definition
Woman's Age	Continuous	Female age in years at time of abdominal myomectomy
Volume of fibroids (pre-op)	Continuous	Cumulative volume of intramural and subserosal fibroids based on preoperative imaging Will be used for stratification and randomization.

Mass of fibroids (post-op)	Continuous	Cumulative mass of intramural and subserosal fibroids based on pathology reports -Will be used to account for variability in final models.
Pre-treatment with Lupron, Depo-provera, OCPs	Dichotomous	Pre-operative treatment with Lupron, Depo-provera or OCP's
Intraoperative treatment with vasopressin or tourniquet	Dichotomous	Use of intraoperative vasopressin or tourniquet during myomectomy.

Other	Type	Definition	Use
Uterus size in weeks gestation	Ordinal	Uterus size in weeks gestation per pre-operative physical exam	Table 1 characteristic
History of Gynecologic Malignancy	Dichotomous	If history of gynecologic cancer (uterine, ovarian or cervical cancer), then yes. If not, then no.	Exclude if yes.
Uterine Anomaly	Dichotomous	If septate, unicornuate or bicornuate uterus, then yes. If abnormality is less severe than arcuate uterus or normal then no.	Exclude if yes.
Prior Cesarean Section Cycle	Dichotomous	If prior Cesarean delivery, then yes. If no prior Cesarean delivery, then no.	Table 1 characteristic, stratum-specific sub-analyses
Gravidity	Count	Number of prior pregnancies	Table 1 population characteristic
Gravid	Dichotomous	If number of pregnancies is 1+, then yes If number of pregnancies is 0, then no	Table 1 characteristic, stratum-specific sub-analyses
Parity	Count	Number of prior pregnancies	Table 1 population characteristic
Living children	Count	Number of living children	Table 1 characteristic
Woman's Age (SART categories)	Categorical	Group by age in years at abdominal myomectomy: <30 30-34 35-37 38-39 40-42 43+	Table 1 population characteristic
Race	Categorical	Group by race: White, Black/Africa-American, Hispanic, Asian/Pacific	Table 1 population characteristic

		Islander, American Indian/Alaskan Native, Middle-Eastern	
--	--	--	--

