2.3 Exploratory Objectives n/a**2.4 Endpoints**

Estimated blood loss as determined by anesthesia and surgeon at time of abdominal or laparoscopic myomectomy, difference between post-operative and pre-operative hemoglobin, post-operative temperature, and overall length of hospital admission.

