4.2 Toxicities and Dosing Delays/Dose Modifications

Given this is a one-time dosing, toxicities will be limited to the immediate intervention period. Any patient who receives treatment on this protocol will be evaluable for toxicity for the entire duration of action of this

medication.

According to published research, serum levels of misoprostol nadir 6 hours following administration and the duration of pharmacologic action is considered to be only 3 hours (3,5). All patients are hospitalized following abdominal myomectomy and laparoscopic such that all patients will be monitored as inpatients for a minimum of 4 hours post-operatively.

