4.6 Duration of Follow Up

Patients will be followed for the duration of their hospital admission following abdominal or laparoscopic myomectomy. Patients will be required to stay a minimum of 4 hours post-surgery. Blood will be drawn right before patient leaves the hospital, post operatively.

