10.2 Sample Size and Accrual

Power calculation based on the standard deviation in published reports (5) demonstrates that enrollment of 25 participants per arm is necessary to detect 1 standard deviation difference with 90% power. Further, published results from pilot studies in this population (7) and demonstrates that enrollment of 25 participants per arm is necessary to detect 0.5g/dL difference in hemoglobin with 90% power.

Prentice Women's Hospital of Northwestern Memorial performed over 100 abdominal myomectomies in 2013. Across a year-long study period, we anticipate identifying a minimum of 70 patients to evaluate our primary hypothesis. We have increased our sample size from 50 to 70 to account for the 9 participants that were either consented by a non-study team member, did not get the study drug due to an error at pharmacy or left the hospital after surgery thus we could not obtain a POD 1 which is needed for data analysis.

Following data collection from at least 20 participants in each arm, standard deviation calculations will be performed to confirm that the standard deviations in our sample population is similar. Power calculation will be repeated using the standard deviations in our active and placebo groups and additional participants will be enrolled as needed to achieve adequate power to evaluate our primary outcome of intraoperative blood loss.

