10.3 Data Analyses Plans

To determine whether women who take a pre-operative dose of misoprostol experience lower blood loss during abdominal myomectomy compared to matched controls who take placebo, we will perform linear regression. We will use this model to assess for the role of numerous covariates, including gravidity, parity and age. Secondary outcomes of percent hemoglobin drop, duration of procedure and length of inpatient hospitalization will be assessed using the T test and further evaluated with multivariate-adjusted linear regression where appropriate. The need for post-operative blood transfusion between groups will be assessed with the Chi-square (Fischer's exact) test. The role of numerous potential covariates will be assessed with Chi-square (Fischer's exact) test for dichotomous variables and T test for continuous variables with $p < 0.05$.

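### Length of stay is given in days with no counting rule, although women may leave 4 hours after surgery, and its planned t test ignores surgical route

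*Combined protocol and SAP*

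**What the plan says.** Section 2.4 names "overall length of hospital admission" among the endpoints, without a unit. The outcome table in section 10.1 has a row "Duration of hospital stay (days", typed as continuous, whose whole definition is "Number of days inpatient following abdominal myomectomy". The text shown gives no clock time for start or end and no rule for counting midnights, calendar days or fractions.

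Section 4.6 sets the shortest stay: "Patients will be required to stay a minimum of 4 hours post-surgery". Section 4.2 agrees: "all patients will be monitored as inpatients for a minimum of 4 hours post-operatively". Section 10.2 gives, as one of several reasons for 9 unusable participants, that some "left the hospital after surgery thus we could not obtain a POD 1 which is needed for data analysis". It does not say how many of the 9 this was.

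For the analysis, section 10.3 states that "length of inpatient hospitalization will be assessed using the T test", with adjusted linear regression to follow where appropriate. The covariates in section 10.1 are age, fibroid volume, fibroid mass, hormonal pre-treatment, and vasopressin or tourniquet use. Surgical route is not among them.

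**The concern.** The definition does not fit the enrolled population. It mentions only abdominal surgery, whereas sections 2.1 to 2.4 and 4.6 cover both routes. Its unit is six times the shortest permitted stay.

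If the analyst counts whole days, two artefacts follow. Women who leave on the day of surgery all get the same score, so a shorter stay among them cannot show. And the hour at which surgery ended can move a patient by a full day with no change in her actual stay.

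Route matters separately. Abdominal and laparoscopic stays are likely to differ by much more than any drug effect, and an unadjusted t test leaves that difference in the error term. With no rule fixed in advance, the choice among midnights, calendar days and hours could also be made after the data are seen.

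**Working it through.** **Plan's own figure.** There is none for stay: no SD, effect, power, route mix or same-day share. The sample size in section 10.2 (25 per arm, 1 SD, 90% power) concerns blood loss. An exact two-sided 5% t test needs 23 per arm, close to the stated 25, but this has no bearing on stay.

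**Step 1: the unit.** The minimum stay is 4/24 = 0.17 day. If days are midnights crossed, the score is floor((clock hour at end of surgery + stay in hours)/24). An 8-hour stay after surgery ending at 11:00 gives floor(19/24) = 0. The same stay after surgery ending at 17:00 gives floor(25/24) = 1. Stays of 4, 8 and 11 hours from 11:00 give floor(15/24), floor(19/24) and floor(22/24), all 0.

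**Step 2: fractional days.** If days means hours/24, the mean difference and its standard error are both divided by 24. The t statistic is unchanged and nothing is lost. The loss therefore depends wholly on the unstated counting rule.

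**Step 3: rounding alone.** Rounding to whole days adds about 1/12 day² to the variance, so n is in effect divided by (SD² + 1/12)/SD². Assume 35 per arm and a true difference of 0.7 SD, for which power without rounding is 82%:

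| Assumed SD of stay (days) | Variance factor | Effective n per arm | Power |
|---|---|---|---|
| 2 | 1.021 | 34 | 81.5% |
| 1 | 1.083 | 32 | 79% |
| 0.5 | 1.333 | 26 | 71% |
| 0.3 | 1.926 | 18 | 55% |

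**Step 4: simulation with route.** All inputs are assumed: 35 per arm; laparoscopic stay mean 9 h (SD 4); abdominal mean 48 h (SD 12); surgery ending 10:00 to 17:00; misoprostol shortening the part of the stay beyond 4 h by 25%; days counted as midnights. There were 2,500 trials per setting, so Monte Carlo error is about 1 point. About 75% of laparoscopic stays score 0. Power, hours v whole days:

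| Laparoscopic share | t test, no route | Linear model with route |
|---|---|---|
| 10% | 81% v 72% | 98% v 92% |
| 50% | 25% v 25% | 88% v 66% |
| 90% | 11% v 14% | 42% v 25% |

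**Step 5: sensitivity.** Changing only the abdominal SD to 24 h gives, with route in the model, 53% v 48% (10% laparoscopic), about 35–38% v 34–37% (50%, range over repeat runs) and 23% v 21% (90%). If the shortening is also cut to 10%, hours and days differ by about a point or less.

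**Step 6: a different model.** Mix same-day and overnight stays, with an effect on overnight stays only and an unadjusted t test. Hours v whole days then give 81% v 82% with no same-day stays, 42% v 34% with 25%, 22% v 17% with 50% and 10% v 8% with 75%. If every stay were same-day, whole days would have no variance and no comparison could be made.

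**Step 7: the effect of route itself.** At half laparoscopic with stay in hours, adding route raises power from 25% to 88% (abdominal SD 12 h), or from 18% to about 35% (SD 24 h). In these settings that exceeds the gain from changing the unit.

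**The case against.** The strongest reply is that no whole-day count is stated. The row is typed continuous, in a table that gives a separate count type to items such as "Number of living children". Fractional days fit the definition and would lose nothing. The data collection sheet is attached to the protocol but not shown here, and may record discharge time. This stands: the tie problem is conditional. The label is weak evidence, however. The next row, procedure duration in minutes and also typed continuous, carries the same day-based definition. Parity is defined as a number of pregnancies. A number of days inpatient reads most naturally as a count, and fractional days would need two clock times that the variable list does not name.

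Second, 4 hours is a floor, not an expected stay, and section 4.2 says all patients are hospitalized. A reader might infer that many women leave the same day. The documents do not support that, since the only evidence is an unstated part of 9 participants.

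Third, a reader might infer that the plan gives up some 20 points of power. It does not follow. That gap appears only with route in the model, a narrow assumed SD and an assumed 25% effect. Under the planned t test hours gain little or nothing at half laparoscopic, and whole days did slightly better at 90%.

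Fourth, sections 1.1 and 1.4 speak of prolonged stay, which days describe well, and days are easy to read. That is a fair reason to report days, but hours keep the long stays as well. The mention of abdominal surgery alone is probably leftover wording, and easily corrected.

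**Conclusion.** The point holds as a minor one. It is established that the stay outcome has no counting rule in the text shown, that its definition names only abdominal cases, that its unit is coarser than the shortest permitted stay, and that route is absent from both the planned t test and the covariate list. That same-day stays tie is conditional on a whole-day count.

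The size cannot be derived from the documents. Under the assumed inputs, the gain from hours over whole days with route in the model runs from no difference to about 20 points (88% − 66% = 22 at most). Without route it is little or nothing when laparoscopic cases are common. That route drives much of the variation in stay is likely, but not documented. Only one secondary comparison is affected; neither the blood-loss analysis nor the sample size depends on it.

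**What to change.** In section 10.1, define the outcome as hours (or exact fractional days) from end of surgery to hospital discharge, for abdominal and laparoscopic cases alike. Name the two recorded times from which it is computed.

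In section 10.3, make a linear regression of that outcome on treatment, with planned route as a covariate, the main analysis of stay. Planned route is preferable to the route actually performed because it is fixed before surgery. Show whole days descriptively. If whole days are kept as the analysed outcome, state the counting rule and use a method suited to ties and skew.

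The cost is one definition, one sentence in the analysis section and two times per patient. An inpatient surgical record can be expected to hold these times, though the documents do not say so. No extra patients or procedures are needed. The small downside is that hours also pick up discharge logistics, which should add noise but, with the arms blinded, should not favour either one. Settle the definition before stay is compared between arms.

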13.0 APPENDICES

13.1

Data Collection Sheet (see attached)

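### In the 10.1 variable table, procedure duration carries the length-of-stay definition and parity carries the gravidity definition

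*Combined protocol and SAP*

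**What the plan says.** The outcomes part of the 10.1 table has two adjacent continuous rows. Their labels begin "Duration of hospital stay (days" and "Duration of procedure (minutes", each followed by a closing bracket. The definition in both rows is the same sentence: "Number of days inpatient following abdominal myomectomy".

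Section 10.3 treats them as different quantities: "Secondary outcomes of percent hemoglobin drop, duration of procedure and length of inpatient hospitalization will be assessed using the T test", with adjusted linear regression to follow where appropriate.

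Later in the same table, the gravidity and parity rows are both counts and both read "Number of prior pregnancies". The text of 10.1 lists parity, with fibroid volume and location, among the things on which randomization is based. Section 10.3 names gravidity, parity and age as covariates whose role the blood-loss regression will assess.

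**The concern.** These are working definitions, from which variables are to be recorded and analysed. A definition in inpatient days under a label in minutes gives the wrong quantity for a named secondary outcome. An analyst who notices the slip must then choose the interval. Incision to closure, time in the operating room and anesthesia time are all possible, and the start and end events differ between abdominal and laparoscopic cases. If that choice is not written down in advance, it is made after the data exist.

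For parity, the question is whether births or pregnancies were recorded under that name. The answer matters for the description of the sample, for the covariate assessment and, if parity was used in allocation, for how women were classified at randomization.

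**Working it through.** The plan gives no figure to reproduce here. The check compares definitions and then follows them through the analyses in 10.3.

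**Step 1. The four rows of the 10.1 table side by side.**

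| Row | Unit or type | Quantity defined | Consistent with label? |
|---|---|---|---|
| Hospital stay | days | inpatient days | yes |
| Procedure duration | minutes | inpatient days | no: wrong quantity and wrong unit |
| Gravidity | count | prior pregnancies | yes |
| Parity | count | prior pregnancies | no: same as gravidity |

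**Step 2. Is there a correct definition elsewhere?** The three secondary objectives in 2.2 concern transfusion, fever and adverse effects. The endpoints in 2.4 cover blood loss and hemoglobin change and end with "post-operative temperature, and overall length of hospital admission". Neither section mentions operative time. Section 10.3 names it without start or end points. The appendix refers to a form, "Data Collection Sheet (see attached", which is not in the supplied text. Section 10.1 says that this form defines fibroid volume, and says nothing of the kind about operative time or parity.

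**Step 3. Consequence for the secondary tests.** Let L be the length-of-stay variable and D the procedure-duration variable. Under the table, D = L for every woman, so the t statistic and p-value for D equal those for L. Section 10.3 lists three continuous secondary outcomes: percent hemoglobin drop, procedure duration and length of stay. Read literally, they contain 3 − 1 = 2 distinct quantities.

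**Step 4. Consequence for the regression.** Let Y be blood loss, T treatment, G gravidity and P parity. If G = P for every woman, their correlation is 1 and a model with both becomes

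E(Y) = b0 + b1·T + b2·G + b3·P = b0 + b1·T + (b2 + b3)·G.

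Only the sum b2 + b3 can be estimated, so the roles of gravidity and parity cannot be separated. The treatment coefficient b1 is the same as in the model with one copy. If the two covariates are instead assessed one at a time, the two fits are identical.

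**Step 5. What does not depend on these rows.** The calculations in 10.2 (25 per arm for a 1 SD difference, and for a 0.5 g/dL hemoglobin difference) and the increase from 50 to 70 use neither procedure duration nor parity.

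**The case against.** The strongest reply is that nobody would be misled. The label, the unit and the separate listing in 10.3 all show that a time in minutes was intended, and parity is a standard obstetric term. The unseen data collection sheet may also define both correctly. Much of this stands, and it rules out several stronger readings:

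- A reader might infer that operative time is not measured. The documents do not support that. They support only that the supplied text gives no valid definition of it.
- A reader might say that one of the plan's three secondary outcomes is undefined. Section 10.3 also tests transfusion, so the count is one of three continuous secondary outcomes, or one of 3 + 1 = 4 with transfusion. Procedure duration is also absent from the objectives and endpoints, which lowers its weight.
- A reader might infer that women were stratified on the wrong count. The text of 10.1 names parity as a basis for randomization, but its explicit stratification sentence names only fibroid volume. Only the volume row is marked for stratification, and the parity row is marked for baseline description. Misclassification would require both that parity was used in allocation and that staff followed the table.
- A reader might infer that the primary regression fails. Section 10.3 does not say that both covariates enter one model. If they did, software would drop one, and the treatment coefficient would not change.
- A reader might infer that length of stay is undefined for laparoscopic cases because the sentence mentions only abdominal surgery. Sections 2.4 and 4.6 cover both routes through the hospital admission, so this looks like leftover wording.

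The reply does not remove the error. The label gives the unit but not the interval, and no supplied text corrects either definition.

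**Conclusion.** Wrong as written, minor severity. One continuous secondary outcome carries another outcome's definition, and one covariate, also named as a basis for randomization, carries another covariate's definition. Copy-paste is the likely cause. The duplicated test in step 3 and the perfect correlation in step 4 are literal readings: they arise in the data only if staff recorded what the table says, which the documents do not show. It is also assumed that the data collection sheet does not already settle the definitions. If it does, the table still has to be brought into line with it. The primary comparison of blood loss between arms and the sample size do not rest on either definition.

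**What to change.** 1. Define procedure duration as minutes between a stated start and a stated end that apply to both abdominal and laparoscopic cases. First incision to skin closure is one example; other conventions would serve if fixed before unblinding.
2. Define parity as number of prior births, distinct from gravidity.
3. Check how parity was recorded for women already randomized, and whether it was used in allocation. Section 10.2 shows that enrollment had begun when the sample size was raised.
4. As a minor consistency edit, extend the length-of-stay definition to abdominal or laparoscopic myomectomy.
5. Confirm that the data collection sheet matches the corrected table.

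The cost is three table cells and a records check. The documents do not say where operative times are held. Taking them from routine surgical records is an assumption to confirm. No clinical procedure changes.
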